take part in the program immediately will be asked to take part in 3 interviews (baseline and then 3 and 6 months after the start of the program. Those in the delayed start group will be asked to take part in 4 interviews (baseline (at the point of signing up for a later program), immediately prior to the beginning of the program and then 3 and 6 months after the start of the program. Standard instruments will be used to assess burden, mood (anxiety and depression), caregiving confidence and mastery, and care recipient well-being.

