addition to sponsor-based debriefings, the semi-structured interviews we will conduct with the interventionists during the Aim 2 and Aim 3 studies will also provide a linkage for them to the overall study and will, hopefully, provide them with a sense of ownership in the developing system.

*Caregivers.* It will only be family caregivers who will be part of the clinical trial component of this study (in Aims 2 and 3). Recruitment into the studies will be through referral from the sponsoring organizations. Each organization will recruit caregivers to take part in Savvy programs provided by interventionists trained in the system we are developing. We will provide organizations with materials they can use to announce Savvy and the studies; we will encourage the organizations to insert these materials into their own standard informational templates (i.e., standard logo and graphics). For caregivers willing to do so, their contact information will be provided to the Emory study team. We will arrange a phone or video call with each during which we will explain the study (Aim 2 or Aim 3 – a caregiver will not be able to take part in both), explain eligibility criteria, and seek informed consent (verbally) for participation. We do not anticipate attrition to be a problem in the Aim 2 study; research contact, following consent, will occur over a very brief period of time. All who consent to the Aim 2 study will take part immediately in a Savvy program and in an on-line survey and (for some) in-person interview conducted by phone or video right after the program. Prolonged retention will be more of a challenge in the Aim 3 study. Those taking part will enter a Savvy program either immediately or after a delay based on scheduling at the individual agencies. For those taking part immediately a series of 3 phone or video interviews will bracket their Savvy participation (at baseline then at 3 and 6 months following baseline. For those with a delayed start, we will conduct 4 interviews (upon sign up, immediately prior to the start of the program and then 3 and 6 months after program completion). To foster engagement with the project, we will prepare and distribute to participants a monthly project newsletter,

featuring tips on exercise and healthy eating and profiles of the study team. We will also send birthday and seasonal holiday cards, as appropriate.

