## **10. Plans for analysis**

Multi-level mixed effects models (MLM) with random (participant) and fixed (cohort) effects will be employed to test for linear (and non-linear) trajectories of change for the Intervention group versus waitlist

group focusing on the group-by-time effect. To address the primary effect of the Savvy intervention, the Immediate group will be compared to the waitlist delay group, using the first 2 time points (0m-2m) to test for differences between the 2 groups' changes post intervention. Additionally, the combined Savvy intervention effects will be assessed using a paired t-test for the combined immediate group's first 2 time points (0m-2m) with the waitlist delay group's 2 time points before and after beginning Savvy (4m-6m). If there are significant differences between the 2 groups at the time point immediately prior to receipt of the intervention, these "baseline" effects will be included and adjusted for a final analysis of covariance (ANCOVA) model for these change scores. Given that the immediate group will have 3 post-intervention measurements (2m-4m-6m), MLM longitudinal models will also be employed to assess the overall time effects plus planned post hoc comparisons for both the immediate intervention effect and the longer term and sustained effects. Sidak Type-I error rate adjustment (which has higher power than Bonferroni) will be applied for the multiple pairwise time point comparisons. The proposed study design also has the advantage of capturing "baseline" time points for the delay group (0m-2m-4m) which will provide an excellent opportunity to evaluate what if any potential "placebo" effects there may be from being enrolled in this type of study. These initial data captured at 0m-2m-4m for the delay group will also be used to evaluate any potential decline occurring during this time period. All model assumptions will be tested; grand mean centering used to help combat multi-collinearity between variables; and standard diagnostic tests and influence statistics used to test the distributions of the residuals. MLM models utilize all available data for all participants at each time point and have the advantage of adjusting for the missing data over time, where repeated measures ANOVAs do not. Further covariate predictors of missingness (mainly due to attrition) over time will be included to additionally adjust for these confounders SPSS v.24 will be used for all analyses at the 5% significance level.

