We will use a meta inference process to answer the central question of this project: Can the system train interventionists to maintain fidelity to core SAVVY principles and demonstrate the ability to tailor the implementation to match cultural values of the community? This inference procedure examines both the process (System Effectiveness Study) and the outcomes (preliminary Efficacy Study). The research team will follow a series of analytic steps to create meaning out of the relatively large amount of collected data, incorporating both the quantitative and qualitative components in a dynamic and interactive manner. We will look first at the results interventionists' ability to provide Savvy faithfully and in a manner congruent with local values: What conclusions or trends do fidelity monitoring, caregiver surveys, and interviews with all parties yield? Next we examine the impact of Savvy on participating caregivers to further establish the effectiveness of the system. If caregiver outcomes improve, this will provide a demonstration that system-trained interventionists can faithfully deliver Savvy in such a manner that its mechanism of action can have an expected effect on caregiver participants. If the outcomes do not support the effectiveness of this new system on either or both questions, we have the data to inform further system development work. The outcome of this process will be a finalized interventionist training system, one informed by a contextual understanding of the effects of the system and ready for a next step, a Stage III or IV intervention trial.

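### The supplementary test of the combined Savvy effect is an uncontrolled pre-post comparison, so change that caregivers would have shown anyway is counted as a program effect

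*Combined protocol and SAP*

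**What the plan says.** Section 10 (Plans for analysis) sets a controlled primary analysis: "To address the primary effect of the Savvy intervention, the Immediate group will be compared to the waitlist delay group", on the difference between arms in change from month 0 to month 2.

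It then says that "the combined Savvy intervention effects will be assessed using a paired t-test". This test takes months 0 and 2 from the immediate arm, and months 4 and 6 from the wait-list arm, whose program starts after the four-month wait. If the arms differ significantly just before their programs, an ANCOVA of the change scores adjusts for that difference.

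The section recognises that outcomes may move without Savvy. The wait-list arm's visits at 0, 2 and 4 months are to show what placebo effects "there may be from being enrolled in this type of study", and the same data "will also be used to evaluate any potential decline occurring during this time period". No rule feeds either result into the combined estimate.

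The section closes with an overall inference: "If caregiver outcomes improve, this will provide a demonstration that system-trained interventionists can faithfully deliver Savvy". It does not name the analysis that decides whether outcomes improved.

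**The concern.** A paired test against zero is a before-and-after comparison. It credits to the program everything that moves caregivers' scores between the two interviews, such as enrolment effects, regression to the mean and secular trend. Decline as the dementia progresses works the other way and hides benefit.

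The randomized design removes such shared change from the primary comparison. The combined test gives that protection up, yet it is described as the effect of the intervention and run at the 5% level. It also has half the standard error of the primary change comparison, so it can be significant when the controlled test is not. Because the closing inference asks only whether outcomes improve, the plan does not stop an uncontrolled gain from being read as evidence that the training system works.

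**Working it through.** **Inputs from the documents.** 120 caregivers (sections 4 and 5); random assignment within each cohort of 20 (Field Methods); windows of 0-2 and 4-6 months and a 5% level (section 10).

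**Not in the documents.** Allocation ratio, sidedness, SD, pre-post correlation *r*, drift, dropout and any power calculation. There is therefore no plan figure to reproduce. Assumed: 60 per arm, two-sided tests, outcome SD 1, *r* = 0.5 to 0.7, drift of 0.10 to 0.20 SD per two-month window, no dropout, no clustering.

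**1. What each contrast estimates.** Let θ be the Savvy effect over two months, and d₁ and d₂ the untreated change in months 0-2 and 4-6.

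- Primary: (θ + d₁) − d₁ = θ.
- Pooled paired: ½(θ + d₁) + ½(θ + d₂) = θ + (d₁ + d₂)/2.

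Equal drift d in both windows gives a bias of d. An enrolment effect confined to the first two months gives d/2. The ANCOVA is triggered only by a pre-program difference between arms, and adjusting for that difference does not remove a common trend.

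**2. Precision at *r* = 0.6.** The SD of a change score is √(2(1 − r)) = √0.8 = 0.894.

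- Paired test: SE = 0.894/√120 = 0.082.
- Primary change comparison: SE = √(0.8 × 2/60) = 0.163.

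With a critical value of about 1.98, the paired test is significant at a mean change of 1.98 × 0.0816 = 0.16 SD. The primary needs a difference of 1.98 × 0.1633 = 0.32 SD.

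**3. Rejection rate of the paired test when θ = 0.** Two-sided noncentral *t*, 119 df, noncentrality = mean change × √120 / √(2(1 − r)). In the lower three rows the mean change is halved.

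| Drift | r = 0.5 | r = 0.6 | r = 0.7 |
|---|---|---|---|
| 0.10, both windows | 19.2% | 22.9% | 28.9% |
| 0.15, both windows | 37.1% | 44.5% | 55.7% |
| 0.20, both windows | 58.4% | 68.1% | 80.1% |
| 0.10, first window only | 8.4% | 9.3% | 10.8% |
| 0.15, first window only | 12.9% | 14.9% | 18.3% |
| 0.20, first window only | 19.2% | 22.9% | 28.9% |

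Simulation of 40,000 trials agrees. At *r* = 0.6 the primary comparison rejects in 5.1% and 4.8% of trials at drift 0.10 and 0.20.

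**4. Masking.** A true benefit of 0.20 SD with a decline of 0.10 SD in both windows leaves a net change of 0.10 SD. Power falls from 58.4% to 19.2% (*r* = 0.5), 68.1% to 22.9% (0.6) and 80.1% to 28.9% (0.7).

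**5. What a controlled combined model would give.** Generalised least squares, visits at 0, 2, 4 and 6 months, 60 per arm, equal correlation between visits, common time effects.

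- *Constant effect after start.* At *r* = 0.6 the immediate-arm weights are −0.375, 0.5, 0.5, −0.375, with signs reversed in the wait-list arm. The squared weights sum to 0.78125 and the weights to 0.25. The variance is (0.4 × 0.78125 + 0.6 × 0.25²) × 2/60 = 0.35 × 2/60, so SE = 0.108 (0.118 at *r* = 0.5, 0.095 at 0.7).
- *Same model when the effect fades.* With effects of 0.4, 0.2 and 0 in the immediate arm and 0.4 at wait-list month 6, it returns 0.5 × 0.4 + 0.5 × 0.2 + 0.375 × 0.4 = 0.45.
- *Effect free by visit since start.* First-visit SE = √((1 − r²) × 2/60) = √(0.64/30) = 0.146 (0.158 at *r* = 0.5, 0.130 at 0.7). Wait-list month 6 gets zero weight.

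**The case against.** **The test is supplementary and the threat is acknowledged.** The randomized comparison carries the primary effect, and the wait-list arm's untreated change will be reported alongside. This stands, and it limits the point to the combined result. It does not correct that result, because no rule links the two.

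**The wording is loose.** The sentence might mean a comparison of the immediate arm's 0-2 month change with the wait-list arm's 4-6 month change, in which case equal drift cancels. But a paired test cannot compare two different groups of people, so pooling is the only coherent reading. On the other reading both sides are treated, so a constant Savvy effect would cancel as well and there would still be no untreated control.

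**Nothing shows the closing inference will use this test.** This is Stage I work on preliminary efficacy with no decision threshold, and caregiver outcomes are considered after fidelity data and interviews. That is true, but the plan leaves the choice open, and a sentence would close it.

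**The rates rest on assumed drift.** They do. At 0.02 SD the rate is under 6%. With 96 complete pairs (also an assumption), the 0.20 SD rates are 49% to 71%. The bias itself needs no assumption about size: it equals the average untreated change.

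**A mixed model is not clearly better.** This largely stands. The constant-effect version can mislead, and the plan itself distinguishes "both the immediate intervention effect and the longer term and sustained effects". The free-effect version's first-visit estimate is in essence the baseline-adjusted primary contrast.

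**Conclusion.** The point holds. The combined paired test estimates the Savvy effect plus average untreated change, and nothing in section 10 removes the second part. Under the stated assumptions its false-positive rate is 19% to 80% for drift of 0.10 to 0.20 SD in both windows, and 8% to 29% if drift is confined to the first two months. These rates are illustrative, since the documents supply none of the inputs on variability or drift.

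The randomized 0-2 month comparison is not affected by change shared by both arms. That covers shared change only: reactions to knowing one's assignment do not cancel. It also presumes that the month-2 visits exist. Field Methods and section 10 use 2, 4 and 6 months, but section 5 gives the wait-list arm interviews "immediately prior to the beginning of the program and then 3 and 6 months after the start of the program", and Recruitment gives them "immediately prior to the start of the program and then 3 and 6 months after program completion". On those two schedules the wait-list arm has no untreated 2-month visit.

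**What to change.** **Needed.** State in section 10 that the pooled paired change is descriptive. State also that any conclusion that caregiver outcomes improved, including in the closing inference, rests on comparisons with the wait list. This costs only wording.

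**Optional, if a combined estimate is wanted.** Reconcile the visit schedules across section 5, Recruitment, Field Methods and section 10 first. Then fit a mixed model to all visits with categorical time common to both arms, a time-varying Savvy indicator, cohort, and random participant and class effects. State its assumptions: common time effects, and an effect that is constant after program start, because nobody is untreated at 4-6 months. As a sensitivity analysis, let the effect vary by visit since start; the first-visit effect then rests only on the randomized comparison with the untreated wait list.

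The price is precision: both models have larger standard errors than the paired test, before any class effects, and the constant-effect version can overstate a fading benefit. It is a trade-off that the sponsor may reasonably decline, provided the wording change is made.

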#### **4. Goals/Aims**

*Aim 1.* Develop a prototype web-based system for Savvy interventionist training and certification and an accompanying performance fidelity monitoring process. Development efforts will yield web-based components delivered through freely available course management and survey applications (e.g., Canvas; Articulate Rise) that will enable sponsoring entities to train and certify interventionists who can locally tailor Savvy, monitor the fidelity of their performance in delivering Savvy, and assess the program's impact on caregivers.

*Aim 2.* Establish the field-readiness of the system. We will engage three community entities serving culturally, ethnically, and geographically diverse constituencies to collaborate with the study team and expert advisory panel in a highly participatory formative test of the prototype system developed through Aim 1 activities. Results and feedback will inform finalization of materials for the Aim 3 trial.

*Aim 3.* Conduct a field trial of the system. The trial will test the effectiveness of the system and examine its preliminary efficacy in producing expected outcomes (i.e. well-being, mastery) in a diverse group of caregivers participating in programs delivered by newly trained interventionists. Six culturally or organizationally diverse sponsors will recruit 2 individuals each to be trained as Savvy interventionists (12 interventionists) and each sponsor will then recruit at least 20 caregivers to take part in a wait-list, no control group study (N=120) of the performance of the interventionists and the preliminary efficacy of the Savvy program provided by them.

The figure below provides a broad timeline for project activities. While we will begin some Aim 2 activities before all of the Aim 1 activities are complete and some Aim 3 activities before all of the Aim 2 activities are complete, we expect Aim 1 activities to be complete by project month 12 and Aim 2 activities to be complete by the end of the second project year.

		Year 1	Year 2	Year 3	Year 4
Project startup activities	Project startup activities	Start			
	Preliminary Syllabus & Materials	Start	End		
	Storyboard Content & Delivery		Start		
	Materials Production		Start		
Recruit/orient 3 organizations	Recruit/orient 3 organizations				
	Train interventionists		Start		
	Interventionists provide Savvy		Start		
	Evaluate & revise		Start		
Recruit 6 organizations	Recruit 6 organizations				
	Train interventionists			Start	

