Results from Savvy participant quantitative fidelity monitoring surveys will be compiled in a simple spread sheet to allow us to see whether there are any notable problems in interventionist performance either within or across sites or in or across interventionists. Likewise, we will be able to compare caregivers' responses about knowledgeability and competence with responses we have received from other caregivers in Savvy programs provided by interventionists who were trained in person by [name] or [name].

Once a cohort of 20 consented caregivers has been formed at any local organization, participants will be assigned (through a random procedure administered by Emory staff) to take part immediately in one of the Savvy programs offered by either of the 2 interventionists or to take part in one of the 2 interventionists' programs after 4 months; follow-up phone or video interviews will be conducted at 2, 4, and 6 months lasting each 1-1.5 hours in length. The audio files from interviews will be saved on Emory School of Nursing's secure share-drive within a password protected folder for 5 years post-study completion.

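### Secondary time-point comparisons: Sidak, chosen for power, gains at most about 0.3 points over Bonferroni; a step-down version at the same 5% familywise error typically gains 2-3 points

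*Combined protocol and SAP*

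**What the plan says.** Section 10 (Plans for analysis) describes the primary test first: immediate against waitlist group, change from 0 to 2 months. It then turns to models over all visits: "Given that the immediate group will have 3 post-intervention measurements (2m-4m-6m), MLM longitudinal models will also be employed". Those models come with "planned post hoc comparisons for both the immediate intervention effect and the longer term and sustained effects", and the adjustment for them is: "Sidak Type-I error rate adjustment (which has higher power than Bonferroni) will be applied for the multiple pairwise time point comparisons". The general level is set by "SPSS v.24 will be used for all analyses at the 5% significance level".

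Three things are left open:

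- **Single-step or step-down.** The text does not say. Single-step is the plain reading of an unqualified Sidak adjustment.
- **Which comparisons form the family.** They are not listed.
- **How many visits there are.** Field Methods agrees with Section 10: "follow-up phone or video interviews will be conducted at 2, 4, and 6 months". Section 5 (Study Design) has a different schedule for the immediate group: "take part in the program immediately will be asked to take part in 3 interviews (baseline and then 3 and 6 months". With baseline, the first schedule has four visits and the second three.

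Sample size comes from Section 4 (Goals/Aims), where each of six sponsors is to "recruit at least 20 caregivers to take part in a wait-list, no control group study (N=120"). No power calculation is given for these comparisons.

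**The concern.** Power is the only reason the plan gives for its choice, so it is fair to ask how much power the choice buys. Against Bonferroni it buys almost nothing. Against a step-down version of the same method it gives some up. Single-step Sidak holds every pair to the strictest threshold even after other pairs have been rejected. It also ignores that pairwise nulls are linked: if any two of four visit means differ, at most three of the six equalities can still be true.

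At stake is the ability to declare the individual longer-term and sustained changes, with about 60 caregivers in the immediate arm (120/2, assuming 1:1 allocation, which the documents do not state).

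**Working it through.** The plan gives no figure for these tests, so there is nothing numerical to reproduce. Its one checkable statement is that Sidak has more power than Bonferroni.

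**Inputs from the documents.** Level 0.05 (two-sided assumed). Four visits give 4×3/2 = 6 pairs; three visits give 3×2/2 = 3 pairs. N = 120.

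**Assumed inputs.** Sustained change of 0.2-0.5 SD; between-visit correlation 0.5-0.7, equal or AR(1); 60 caregivers in the arm, or 48 (20% loss: 60×0.8).

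**Step 1. Sidak against Bonferroni.** Per-test level is 0.05/m for Bonferroni and 1 − 0.95^(1/m) for Sidak.

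| Pairs | Bonferroni | Sidak | Sidak gain at 50% power | at 90% power |
|---|---|---|---|---|
| 3 | 0.01667 | 0.01695 | 0.25 points | 0.11 points |
| 6 | 0.00833 | 0.00851 | 0.29 points | 0.13 points |

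For six pairs the two-sided critical values are 2.638 and 2.631. At 50% power the gain is about (2.638 − 2.631) × 0.399 ≈ 0.003, or 0.3 points. In simulations of correlated pairwise contrasts it ran from 0.0 to 0.30 points.

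**Step 2. Step-down thresholds.** Order the p-values from smallest, compare each with its threshold, and stop at the first failure. Each threshold is 1 − 0.95^(1/j).

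- Holm-Sidak uses j = 6, 5, 4, 3, 2, 1: 0.0085, 0.0102, 0.0127, 0.0170, 0.0253, 0.05.
- Shaffer's counts use the largest number of nulls that can still be true. Among four means the number of true equalities can only be 0, 1, 2, 3 or 6, so j = 6, 3, 3, 3, 2, 1: 0.0085, 0.0170 three times, 0.0253, 0.05.
- Among three means it can only be 0, 1 or 3, so j = 3, 1, 1: 0.0170, 0.05, 0.05.

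No threshold is below the single-step value, so a step-down test rejects everything that single-step Sidak rejects.

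**Step 3. Error rate.** In simulation with four visits, familywise error with all nulls true was 4.2-4.3%. With some nulls true the step-down tests reached at most about 5.2%, which is 5% within simulation error.

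**Step 4. Average power over the true differences.** Paired t-tests on complete data, 20,000 trials per setting. As an analytic check on the first row, the noncentrality for one pair is 0.3×√60/√(2×(1 − 0.7)) = 3.00. With 59 degrees of freedom and a critical value of 2.722, power is 0.611, against 0.607 simulated.

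| Setting | Sidak | Holm-Sidak | Shaffer | Gains (points) |
|---|---|---|---|---|
| 4 visits, sustained 0.3 SD, n=60, r=0.7 | 0.607 | 0.639 | 0.677 | 3.2; 7.0 |
| 4 visits, sustained 0.3 SD, n=48, r=0.6 | 0.352 | 0.373 | 0.408 | 2.1; 5.6 |
| 4 visits, sustained 0.4 SD, n=60, r=0.5 | 0.648 | 0.679 | 0.717 | 3.1; 6.9 |
| 4 visits, sustained 0.5 SD, n=60, r=0.5 | 0.869 | 0.892 | 0.912 | 2.3; 4.3 |
| 4 visits, sustained 0.3 SD, n=60, AR(1) 0.7 | 0.405 | 0.428 | 0.464 | 2.3; 5.9 |
| 4 visits, linear to 0.5 SD, n=60, r=0.7 | 0.483 | 0.537 | 0.551 | 5.4; 6.8 |
| 3 visits, sustained 0.3 SD, n=60, r=0.7 | 0.708 | 0.742 | 0.787 | 3.4; 7.9 |

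At a sustained 0.2 SD (4 visits, n=48, r=0.6) the gains fall to 0.8 and 2.4 points.

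A wider grid of 216 settings for Holm-Sidak gave gains of 0.0 to 9.7 points, median 2.0. In the 103 settings where Sidak's average power lay between 30% and 90%, they ran from 1.9 to 9.7, median 2.9.

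**Step 5. Where the gain falls.** In the first row the chance of detecting at least one true difference was 0.843 under all three methods. The chance of detecting all of them rose from 0.35 (Sidak) to 0.47 (Shaffer). In the three-visit row it rose from 0.56 to 0.72.

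**The case against.** The strongest reply is that nothing here is wrong. Sidak is a valid familywise adjustment and the plan's sentence about Bonferroni is correct. That stands: the point exchanges one valid method for a more efficient one.

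A reader might infer more than the documents support:

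- **That the change is free.** It is not. Single-step Sidak has simple matching simultaneous confidence intervals and the step-down tests do not. In a study of preliminary efficacy, intervals may matter as much as rejections. The plan does not promise simultaneous intervals, so the loss is small, but it is real.
- **That Sidak forfeits most of the available power.** It keeps 0.607/0.677 = 90% of Shaffer's power in the first row and 0.352/0.408 = 86% in the second.
- **That a gain of several points is a property of this plan.** The effect size, correlation and attrition are all assumed. The simulations also use complete-data paired tests, whereas the plan uses mixed models with missing data.
- **That all six pairs are certainly tested.** Planned contrasts for immediate and sustained effects could be fewer. Shaffer's all-pairs thresholds would then not apply, although Holm-Sidak would still work with the smaller count.

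It is also fair to say that the unfixed family matters more than the choice within it: until the contrasts and visits are settled, no threshold can be computed under any method.

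**Conclusion.** The point holds as an optional efficiency improvement. Sidak's advantage over Bonferroni is real but at most about 0.3 points. At the same 5% familywise error, Holm-Sidak typically adds 2-3 points of average power (about 1 at a 0.2 SD effect), and Shaffer's counts add about 2-8.

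These sizes rest on 48-60 caregivers in the arm, the effect sizes and correlations listed above, a single-step reading of the text, and (for Shaffer) a family of all pairs. The benefit is in how many true differences are declared, not in whether any is found.

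It would be a mistake to read this as a flaw in the efficacy test. Section 10 assigns the primary effect to a separate between-group comparison of 0-2 month change, which is not said to belong to the Sidak family.

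**What to change.** 1. Reconcile the visit schedule in Section 5 with Field Methods and Section 10, so that the number of time points is fixed.
2. List the time-point contrasts that form the family for each outcome.
3. Replace the Sidak sentence with step-down Holm-Sidak at 5% familywise error over the listed contrasts. If all pairs are tested, the Shaffer thresholds in Step 2 of the working may be used instead.
4. Report unadjusted confidence intervals, labelled as such, and say that they need not agree with the step-down decisions.

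The cost is a few lines of text and, for each outcome, sorting at most six unadjusted p-values outside the SPSS output. Matching simultaneous confidence intervals are given up. No extra participants or visits are needed.
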